### **Veterans with PTSD lose less weight in VA's weight management program, *MOVE!*.**

Implemented in VA in 2006, *MOVE!* is an evidence-based program for obesity management. The curriculum uses cognitive-behavioral techniques like goal setting and self-monitoring and applying autonomy-supporting counseling like motivational interviewing mostly in in-person group sessions. Nearly 20% of those who participated in at least two sessions lost  $\geq 5\%$  baseline weight at six months, an amount associated with reduced CVD and diabetes risk. Rates of clinically meaningful weight loss nearly double (31.6%) for the 14% of *MOVE!* patients with "intense and sustained" participation ( $\geq 8$  sessions four-to-six months after enrollment). While promising, [name] found that among those with intense and sustained participation, compared to those without mental health conditions, Veterans with PTSD were less likely to lose a clinically meaningful amount of weight (23.7% vs. 28.7% at 6 months; aOR=0.89; p=.008) and lost significantly less total weight at 6 and 12 months.

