**Key Preliminary Study: MOVE!+UP, a tailored weight loss program for overweight Veterans with PTSD, may address MOVE!’s limitations while also improving PTSD symptoms among Veterans with PTSD.** Funded by PI [name] 5-year HSR&D Career Development Award (CDA), we built upon [name] clinical and research expertise in PTSD and health behavior change to develop MOVE!+UP, which addresses the unique barriers to weight loss for Veterans with PTSD. We piloted MOVE!+UP with five cohorts (total N=44), modifying it between each cohort based on quantitative and qualitative data. Initially, MOVE!+UP was led by a peer support counselor in recovery from mental illness, a model that can improve weight and other health and psychosocial outcomes, with strong VA support. Originally, MOVE!+UP was designed to augment MOVE! with four in-person group and six brief phone counseling sessions. Cohorts 1-4 were satisfied, and had modest improvements in physical activity, diet quality and PTSD. However, despite substantial efforts to promote MOVE! engagement to obtain general weight management support, few were willing to attend, contributing to modest weight loss (-1.8 pounds). Many requested MOVE! be integrated with MOVE!+UP’s highly-valued PTSD content. While participants appreciated the peer counselor’s support, they requested health professional involvement to address specialized PTSD and weight loss needs.

Based on data from cohorts 1-4, we made substantial changes to MOVE!+UP, and re-piloted the final package with cohort 5 (n=8 Veterans), whose data are presented below and suggest **MOVE!+UP is acceptable and may improve weight and PTSD symptoms for Veterans with PTSD.** The final MOVE!+UP program is co-led by a psychologist with specialized PTSD training, and

Table 1. Cohort 5 16-Week Weight, PTSD, and Engagement

Weight and PTSD outcomes	Mean (SD) or %
Total weight lost, pounds*	13.9 (4.0)
% baseline weight lost	6.1 (2.1)
% lost ≥ 5% baseline weight	71%
PTSD symptom severity (range: 0-80)*	-17.9 (12.2)
MOVE!+UP sessions attended	
In-person group (16 total)	10.5 (4.4)
% attended ≥ 8 sessions	75%
% of MOVE!+UP walks attended	95%
Dietician visits (2 offered)	1.8 (0.5)
Telephone calls (as needed)	2.6 (1.7)

\*p<.05 change from baseline to 16-week follow-up

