**Manually tracked and administrative data utilization, and process variables.**

For Aim 3, which seeks to place Aim 1 and 2 findings in context and identify areas needing refinement for future implementation, we will capture various process and administrative data.

1. *Intervention only: MOVE!+UP* group and phone session attendance, no shows, and cancellations, including participation in the walks and reasons for non-participation in any aspect of *MOVE!+UP* sessions.
2. *Intervention only:* We will assess time and costs associated with all *MOVE!+UP* activities. Personnel time will be captured during start-up activities like initial training, and once *MOVE!+UP* is running, for one week each quarter, modeled prior research. Research and clinical personnel will enter time spent that week on *MOVE!+UP* training, recruitment, supervision, delivery, and documentation into a system developed by Liu et al. To estimate personnel costs, we will multiply hours each research and clinical personnel spent by their hourly wage rate, as recorded in the VA Personnel and Accounting Integrated Data, or imputed using Bureau of Labor Statistics data. Co-I [name] is applying these methods to analyze implementation costs in a QUERI partnered evaluation. Facilitators and research staff also provide observations and input throughout the course of the study to further assess and inform implementation= (in secure SFFX folder).
3. *For intervention only:* The following information was collected on a basic spreadsheet (see weight goal tracker: weigh-in weights; physical activity and diet quality goals and goals progress (whether meeting them fully, partially, or not); and any additional relevant information in an open-ended comments box. We also copied, scanned, and provide feedback on weekly diet and activity logs, again to be used for clinical purposes and to be evaluated as an exploratory diet quality measure. Both the activity/diet log copies, and the weekly weight/goal tracking documents were stored securely in a locked cabinet, with only a subject ID listed.

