4. *For all participants:* We will capture CDW/CPRS administrative utilization data from 12 months prior to baseline through 12 months post-baseline, including *MOVE!* visits, dietitian visits, primary care, mental health group and individual psychotherapy, and psychiatry care. We also will assess prescription of psychiatric and obesogenic and leptogenic medication from VA pharmacy files. Outpatient utilization will be drawn from administrative data, classified using an algorithm developed by a study team including Co-I [name] that defines groupings of CPT codes and provider specialty codes. Inpatient care will include all cause, psychiatric, and ambulatory care-sensitive condition hospitalizations, as identified in prior studies. We also

will pull bariatric surgery from the EHR from baseline through 12 months post-enrollment to be included in a previously planned sensitivity analysis.

If the trial is positive, costs for encounters in these categories will be measured using the VA Managerial Cost Accounting (MCA) system, adjusted for inflation. We also will capture # of Veterans eligible, ineligible, contacted, recruited and retained, and psychiatric and medical conditions associated visits in the year prior to and 12 months following enrollment (pulled through administrative data).

Starting with cohort 4, we informed participants at enrollment into the study that administrative data will be pulled even if they cease participation in the study, to ensure we have sufficient power to conduct exploratory analyses examining these administrative data-based outcomes, while introducing no additional burden to study participants.

For participants from cohorts 1-3 who withdrew from the study, administrative data will be pulled up through the date of withdrawal. However, participants from cohort 2 and 3 were asked whether they were willing to allow us to pull data from the medical record through 15 months using our phone script. We documented their response in a NTF, submit it to the IRB, and document their decision in our database.

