## 5.6.b. Data Analysis

**Power and Sample Size Calculations.** This study is powered on weight change at six months, comparing intervention and control conditions. We used formulas specified by Friedman et al. for use in clustered randomized controlled designs. Sample size was calculated for continuous outcomes and inflated to account for clustered randomization, using the inflation factor  $1 + (m - 1)\rho$  for cluster size  $m$  and intraclass correlation  $\rho$ , and attrition. Based on outcomes in prior weight loss trials, **we expect those in *MOVE!+UP* to lose 12 pounds on average, which would likely correspond to clinically meaningful weight loss (5% of baseline weight).** The specified expected weight loss is plausible, given *MOVE!+UP* pilot participants lost an average of 14 pounds, corresponding to 6% of baseline weight. We expect those in the control condition to achieve weight loss of 3.6 pounds on average consistent with Veterans with PTSD who participate in *MOVE!*, according to administrative data.

In the power calculation, the standard deviation of the outcome was assumed to be 13 based on previous findings. We calculated this value based on the marginal SD of 50 for baseline weight observed among Veterans with PTSD in *MOVE!*, between baseline and 6-month weight observed in the *MOVE!+UP* pilot (comparable to other weight loss effectiveness trials). Comparing these outcomes, an 8.4 pound difference in weight lost corresponds to prior behavioral weight loss trials and would yield a medium Cohen's  $d$  effect size of 0.65.

Table 7 displays the sample size required for varying cluster sizes *m* and intraclass correlation coefficients  $\rho$  assuming 90% power. The sample size of N=164 total Veterans (82 Veterans per treatment arm) chosen for this study assumes an ICC of 0.03, cluster size of 8 Veterans per randomized group, 90% power, a two-sided  $\alpha$  of 0.05, and a 6-month attrition rate of 25%, similar to MOVE!+UP pilot’s overall retention and a meta-analysis of missing data in weight loss RCTs. We will also be powered to detect a meaningful change in PTSD symptoms in the intervention condition at six months, aligned with the average PTSD symptom reduction of 18 (SD=12) observed among MOVE!+UP pilot cohort 5 participants and assuming a 9-point clinically meaningful reduction in the control condition.

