**Table 7. Sample size considerations for MOVE!+UP hybrid type 1 trial**

ICC ( $\rho$ )	Cluster size (m)	Total Sample Size
0.05	10	196
0.05	8	182
0.03	10	172
0.03	8	164
0.01	10	148
0.01	8	144
Note: assumes a two-sided $\alpha$ 0.05, 90% power, a 12 – 3.6 = 8.4 lb difference in weight loss between groups, a weight change SD of 13, a 0.97 within-person correlation, and 25% attrition. The bolded row displays the selected parameters for the proposed study.		

**Quantitative Statistical Analysis Overview: Aims 1 and 2.** We will use intent-to-treat analyses to assess differences between intervention and control arms. We will use mixed effects models to account for clustering since participants in the intervention arm in the same enrollment cohort receive group treatment together. We will attempt to reduce attrition and missing data, which can lead to selection bias.

**Missing data.** In descriptive analyses, we will report summary statistics on proportion of patients with missing data in each of the study arms. We will report overall rates of missing data as well as specific rates for important variables such as study outcomes and baseline adjustment variables. We will provide descriptive statistics summarizing associations between available auxiliary variables and missingness in important model variables.

Methods for handling missing data in the primary analyses will be pre-specified and not influenced by the descriptive analyses described above. Missing data in the primary and secondary analyses will be accounted for through multiple imputation (MI) methods described below. Prior to multiple imputation, we will attempt to fill in missing baseline values of African-American race/ethnicity from the EHR.

Analyses of primary and secondary outcomes will account for missing data in outcome or baseline adjustment variables through Multiple Imputation (MI). We will perform MI using the Multiple Imputation by Chained Equations (MICE) method. MICE is a general purpose MI method that can handle missingness in variables of mixed data types (e.g. continuous and categorical) as well as

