clustered data. Missing values will be imputed separately for each faux treatment group. MI will be performed using the outcome and baseline variables pre-specified for adjustment, and pre-specified auxiliary variables that are either likely associated with missingness and/or the outcome (gender, age, race, employment status, educational attainment, medication usage associated with a) substantial weight loss or b) substantial weight gain). We will create 50 imputed datasets, which will then be analyzed and combined according to Rubin’s rules for multiple imputation.

MICE requires specifying a statistical model to generate predictions for each variable with missingness. Table 9 lists the statistical models for each variable that will be used in the imputation procedure. Final imputed values will be based on the predictive mean matching approach, which can provide more plausible values when the distribution of a variable exhibits features such as bimodality or skewness.

Imputation Models

Variable Name	Variable Type	Statistical Model for MICE procedure	Rationale for inclusion
6-month Weight	Continuous	Linear regression	Outcome being imputed
Baseline Weight	Continuous	Linear regression	Typically associated with outcome
African-American race/ethnicity	Binary	Logistic regression	Typically associated with outcome and with missingness in a prior WL trial among Veterans
Employment status	Categorical	Multinomial regression	Associated with missingness in a prior WL trial among Veterans
Educational achievement	Categorical	Multinomial regression	Associated with missingness in a prior WL trial

 Citation: <https://www.ncbi.nlm.nih.gov/pmc/articles/PMC6408317/>

			among Veterans
Age	Continuous	Linear regression	Associated with missingness in a prior WL trial among Veterans
Gender	Categorical	Multinomial regression	Typically associated with outcome and was associated with missingness in a prior WL trial among Veterans
Weight management medication usage in the 6 mos following enrollment (Yes vs. no)	Binary	Logistic regression	Typically associated with outcome
Weight gain meds in the 6 mos following enrollment (Yes vs. no)	Binary	Logistic regression	Typically associated with outcome

**References:** Prior WL trial among Veterans: <https://jamanetwork.com/journals/jama/fullarticle/2799407>; [name] will add references for gender, Af-Am race

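### The imputation model for 6-month weight omits programme attendance, which meets the plan's own rule for auxiliary variables and is already collected; the primary effect may be modestly biased

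*Combined protocol and SAP*

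**What the plan says.** Section 5.6.b commits to intent-to-treat: "We will use intent-to-treat analyses to assess differences between intervention and control arms". It assumes 25% attrition at 6 months and fills missing outcomes by chained equations with predictive mean matching and 50 imputations. The work is done separately within strata that it calls faux treatment groups, a term the text does not define.

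The imputation model takes the outcome, the adjustment variables and "pre-specified auxiliary variables that are either likely associated with missingness and/or the outcome (gender, age, race, employment status, educational attainment, medication usage" linked to substantial weight loss or gain. The Imputation Models table lists the same variables. The two medication indicators cover the 6 months after enrollment, so the list is not confined to baseline. Attendance does not appear.

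The same section fixes the primary missing-data method in advance and says the descriptive comparisons will not influence it. The statistical models table has one missing-data sensitivity analysis. It enters the auxiliary variables as covariates, plus any that look associated with a missing 6-month weight. It does not name attendance and leaves the primary imputation as it is.

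Attendance is available. Section 5.5 tracks MOVE!+UP "group and phone session attendance, no shows, and cancellations". For everyone, "We will capture CDW/CPRS administrative utilization data from 12 months prior to baseline through 12 months post-baseline", and this includes MOVE! visits.

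**The concern.** The plan admits auxiliaries linked to missingness or to the outcome. Its own background puts attendance in the second group. In the Introduction, nearly 20% of MOVE! participants with at least two sessions lost 5% or more of baseline weight. For the 14% with intense and sustained participation the text reads "Rates of clinically meaningful weight loss nearly double (31.6" per cent). In pilot cohorts 1 to 4, where standard MOVE! was offered alongside, "few were willing to attend, contributing to modest weight loss".

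Without attendance, a Veteran who stopped after two sessions is matched to observed participants of similar weight, demographics and medication use, whatever their attendance. If people who stop attending are also likelier to miss the 6-month weigh-in, those donors attended more than the person being imputed. The imputed mean loss in that arm is then too large. If this happens to different degrees in the two arms, the difference enters the treatment coefficient of the single primary test. Because the primary method is fixed in advance, attendance cannot be added after the descriptive comparisons.

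**Working it through.** **Plan's own figure.** Per arm, 2 × (13 × (1.960 + 1.282) / 8.4)² = 50.33. Multiplying by the design effect 1 + 7 × 0.03 = 1.21 gives 60.9. Dividing by 0.75 gives 81.2, rounded up to 82, so 164 in total, as in Table 7. This point does not change the sample size.

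**Inputs from the documents.** Expected losses 12 and 3.6 lb; SD 13 lb; 25% missing (no figure by arm); at least 8 sessions attended by 75% (pilot cohort 5, n=8) versus 14% (MOVE! administrative data).

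**Assumptions.**
- MOVE!+UP non-attenders lose 6 lb. Attenders then lose (12 − 0.25 × 6) / 0.75 = 14 lb, a gap of 8 lb.
- Control gap, from 31.6% versus 20% on a normal scale: (−0.479 + 0.842) × 13 = 4.7 lb.
- The odds ratio (OR) for a missing weight, non-attender versus attender, is not in the documents and is varied from 2 to 8.

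**Is an 8 lb gap compatible with the pilot?** Cohort 5's weight loss had SD 4.0 lb. A 6/2 split with gap g and no other variation has SD g × √(1.5/7) = 0.463g, so g can be at most 4.0 / 0.463 = 8.6 lb. If only seven had weights (71% suggests 5 of 7), a 6/1 split caps g at about 10.6 lb. A gap of 8 lb fits both.

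**Formula.** Let p be the share attending, and a and b the missingness probabilities for attenders and non-attenders. Solve p·a + (1 − p)·b = 0.25 with odds(b) = OR × odds(a). Among those observed, p_obs = p(1 − a)/0.75. Imputation that ignores attendance reproduces the observed mean, so each arm's bias is (p_obs − p) × gap. The bias in the effect is intervention minus control.

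| OR | MOVE!+UP: p_obs, bias | Control: p_obs, bias | Net | % of 8.4 lb |
|---|---|---|---|---|
| 2 | 0.785, 0.28 lb | 0.158, 0.09 lb | +0.19 lb | 2% |
| 4 | 0.822, 0.57 lb | 0.170, 0.14 lb | +0.43 lb | 5% |
| 8 | 0.857, 0.86 lb | 0.178, 0.18 lb | +0.68 lb | 8% |

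Check at OR 8 in MOVE!+UP: a = 0.143 and b = 0.571, and 0.75 × 0.143 + 0.25 × 0.571 = 0.25.

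**Higher control attendance.** The 20% group contains the 31.6% group. Removing that overlap gives (0.20 − 0.14 × 0.316)/0.86 = 0.181 and a control gap of 5.6 lb. With that gap and an assumed 30% control attendance, the net bias is +0.09, +0.24 and +0.43 lb at OR 2, 4 and 8 (1% to 5%).

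**Sign.** Take 50% attendance and an 8 lb gap in both arms, with 20% attenders among the missing. The net bias is then 0.80 − 0.80 = 0 at 25%/25% missing (MOVE!+UP/control). It is 0.42 − 1.29 = −0.87 lb at 15%/35%, and +0.87 lb at 35%/15%.

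**Does adding attendance help?** Simulation used predictive mean matching within arm: 82 per arm, 10 imputations, 600 runs, no clustering, true effect 8.4 lb.

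| Scenario | Without attendance | With attendance |
|---|---|---|
| 75%/14% attendance, 8 lb gap | 9.49 | 8.68 |
| Equal attendance and missingness | 8.54 | 8.51 |
| More control dropout | 7.01 | 8.17 |
| No gap | 8.37 | 8.41 |

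These runs were set up separately from the odds-ratio range above. I read them for the direction of the correction, not for the size of the bias.

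**The case against.** A reader might infer that dropouts are given attenders' weight loss and that the intent-to-treat effect is therefore overstated. The documents support neither step. Donors are all observed participants in the stratum, and non-attenders can be among them. Section 5.2 pays for assessments but not for sessions, and it describes a lost-to-follow-up protocol. The sign depends on missingness, attendance and weight gap by arm, and none of these is given for this trial.

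A reader might also take the 1.8 lb lost in cohorts 1 to 4 as the loss of a MOVE!+UP non-attender, and so reach biases of 10% or more. That figure is the mean of all participants in an earlier version of the programme, with four group sessions and six calls. Comparing it with cohort 5 compares programme versions. It would also imply attenders losing (12 − 0.25 × 1.8)/0.75 = 15.4 lb, a gap of 13.6 lb. A 6/2 split then has SD 0.463 × 13.6 = 6.3 lb, against the 4.0 lb observed. Those larger figures should not be used.

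Two further objections stand in part. The 14% for controls comes from routine care, whereas section 5.5 has trial controls scheduled directly into MOVE! with reminder calls and letters. The 75% rests on eight people. Both make the size uncertain, and higher control attendance shrinks it. The planned missing-data sensitivity analysis is relevant but no substitute: it does not name attendance, and entering attendance there as a covariate would condition on a post-randomisation mediator.

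**Conclusion.** The omission is real and does not follow from any rule in the plan. It makes missing at random harder to defend and may bias the primary coefficient. The bias is probably upward if attendance and its link to weight are stronger in MOVE!+UP, and near zero or downward under other patterns. On inputs compatible with pilot cohort 5, it is about 0.2 to 0.7 lb, or 2% to 8% of 8.4 lb. Against a simulated pooled standard error of about 2.41 lb, that is at most 0.68/2.41 = 0.28 standard errors. The range rests on the assumed odds ratio, the 6 lb assumption for non-attenders, equal 25% missingness and 14% control attendance. It does not show that the trial's result will be overstated. The case for the change is that it is cheap and moved the estimate toward the truth in both affected simulated scenarios, with essentially no change where attendance had no link to weight.

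**What to change.** Add attendance to the Imputation Models table, entered within randomised arm: MOVE!+UP group sessions attended (0 to 16) in the intervention arm, and MOVE! visits from baseline to 6 months in control. Use it in the imputation step only. Keep it out of the primary model, so that the coefficient remains the intent-to-treat effect, and out of the covariates of the missing-data sensitivity model. Do the same for the 12-month weight and the PTSD imputations.

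Define the imputation strata. If a faux treatment group means a cluster of about 8, 25% attrition leaves about 6 observed weights in each. In that case run this imputation by arm, so that the extra predictor can be supported.

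The cost is one or two table rows, using data already collected. In a separate simulation (87 per arm, normal-model imputation by arm) the pooled standard error went from about 2.41 to between 2.41 and 2.51 lb, a rise of 0% to 4%. One limit needs stating: for withdrawals in cohorts 1 to 3 without extended permission, administrative data stop at withdrawal, so control visits are known only to that date.
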